10.2.2 Collection and Reporting of SAEs

When an SAE occurs through the AE collection period it should be reported according to the following procedure:

A Takeda SAE form must be completed, in English, and signed by the investigator immediately or within 24 hours of first onset or notification of the event. The information should be completed as fully as possible but contain, at a minimum:

- A short description of the event and the reason why the event is categorized as serious.
- Subject identification number.
- Investigator's name.

CONFIDENTIAL

- Name of the study medication(s)
- Causality assessment.

The SAE form should be transmitted within 24 hours to the attention of the contact listed in Section 1.1. The investigator should make sure the success of the reporting transmission.

Any SAE spontaneously reported to the investigator following the AE collection period should be reported to the sponsor if considered related to study participation.

Reporting of Serious PTEs will follow the procedure described for SAEs.

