including diagnostic and therapeutic interventions, will be made by and conducted at the discretion of the participating study physicians according to their clinical judgement and the local standard of medical care. It is recommended to monitor patients every 12 to 24 weeks in the treatment guideline issued by China Ministry of Health [1]. The procedures are summarized in the Schedule of Study Procedures (Appendix A). All subjects will be followed up annually after the last dose of leuprorelin until stable puberty is reached. Stable puberty is defined as 96 weeks after menarche for girls, or secondary sexual characteristics development of Tanner staging V for boys. At each visit, the following data will be collected if it is reported in the patients medical record: Tanner staging evaluation, height and weight measurement, menstrual history assessment and pelvic ultrasonography for girls.

Figure 3.a Schematic of Study Design

V=visit, D=day, Wk=week, SV=Screening Visit, EOS= End of Study, ET=Early Termination.

A schedule of assessments is listed in Appendix A**Error! Reference source not found.**

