### **6.5.1. Adverse Events**

Adverse events, including SAEs, are recorded in the eCRFs. AEs observed during the treatment period will be classified as treatment emergent adverse events (TEAEs) while those recorded during the follow-up period will be classified as clinical events. Each AE will be coded to system organ class (SOC) and preferred term (PT) using the Medical Dictionary for Regulatory Activities (MedDRA).

TEAEs are defined as AEs with onset occurring during the treatment phase and/or within 30 days (onset date – last date of dose +1≤ 30) after last study drug administration. However, for subjects that continue into the follow-up period, TEAEs will include all AEs up to the Week 100 visit. Clinical events will be any AE with onset after the Week 100 visit.

In general, AEs may be analyzed one of two ways. First method (subject count) is to report the count and percent of subjects reporting the AE. In this analysis a subject is only counted 1 time for the specific AE, and the percentage is with respect to the number of subjects in that safety set. For the treatment period the safety set is all subjects who receive at least 1 dose of study drug. For the follow-up period the safety set will be all subjects with at least 1 follow-up visit after the Week 100 visit. Second method (event count) is to count all events, for the specific AE, and calculate the rate per 100 patient years. Patient years (no. of days/365.25) for the treatment period will be determined from Day 1 to date of the Week 100 visit; patient years in follow-up period will be determined, at the subject level, from date of the Week 100 visit to date of last contact.

An SAE is defined as any untoward medical occurrence that, at any dose:

1. Results in DEATH.
2. Is LIFE THREATENING.

The term “life threatening” refers to an event in which the subject was at risk of death at the time of the event; it does not refer to an event that hypothetically might have caused death if it were more severe.
3. Requires inpatient HOSPITALIZATION or prolongation of existing hospitalization.
4. Results in persistent or significant DISABILITY/INCAPACITY.
5. Lead to a CONGENITAL ANOMALY/BIRTH DEFECT.
6. Is an IMPORTANT MEDICAL EVENT that satisfies any of the following:
  - a. May require intervention to prevent items 1 through 5 above.
  - b. May expose the subject to danger, even though the event is not immediately life threatening or fatal or does not result in hospitalization.

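### The follow-up set for subject-count AE tables requires a later visit, so a child who dies or has a serious event and never attends is left out, although other outputs can show the event

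*SAP*

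**What the plan says.** SAP 6.5.1 describes two ways to analyse adverse events and applies both in each study period.

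- **Subject count.** Each child is counted once per event type, and "the percentage is with respect to the number of subjects in that safety set". In the treatment period no later visit is needed: "For the treatment period the safety set is all subjects who receive at least 1 dose of study drug". The follow-up period has a different condition: "For the follow-up period the safety set will be all subjects with at least 1 follow-up visit after the Week 100 visit".
- **Event count.** "Second method (event count) is to count all events, for the specific AE, and calculate the rate per 100 patient years". In follow-up, "patient years in follow-up period will be determined, at the subject level, from date of the Week 100 visit to date of last contact". This description states no visit condition.

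The follow-up event window opens at once: "Clinical events will be any AE with onset after the Week 100 visit".

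SAP 6.5.1 also repeats the SAE and non-serious AE analyses with both phases pooled, without stating a denominator, and plans listings of all AEs and SAEs. The opening of SAP 6.5 says that safety data use the safety analysis set, which SAP Section 5 defines as all enrolled and dosed subjects.

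SAP Section 3 expects check-ups at least every 24 weeks during follow-up. After treatment ends the schedule is annual: "All subjects will be followed up annually after the last dose of leuprorelin until stable puberty is reached". Information can reach the sponsor without a visit, under Protocol 10.2.2: "Any SAE spontaneously reported to the investigator following the AE collection period should be reported to the sponsor if considered related to study participation".

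**The concern.** Membership of the follow-up set depends on something that happens after the risk period has opened, namely attendance at a visit. The events most likely to prevent attendance are death and serious illness. A child with such an event can be at risk, and known to the sponsor, yet never qualify for the set.

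At stake is the subject incidence of late events. These are likely to be few, so one or two cases can change what the table says. A second consequence is internal disagreement: a death before any visit could be one event in the rate table and no subjects in the incidence table for the same period.

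**Working it through.** The plan gives no figure to reproduce. The sample size of about 300 has no formula behind it, and the number expected to continue into follow-up is not stated.

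**Step 1. How long is the gap before a first visit?**

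- On treatment: 24 weeks = 168 days. SAP Table 6.a allows ±28 days, so up to 168 + 28 = 196 days after the Week 100 visit.
- Last dose at Week 96: taking a year as 52 weeks, the first annual visit is at 96 + 52 = Week 148, which is 148 − 100 = 48 weeks after the Week 100 visit.
- The 30-day TEAE rule hardly covers this gap. With the last dose on Day 672, it reaches Day 672 + 29 = 701, one day after a nominal Day 700 visit. For children who continue into follow-up, SAP 6.5.1 ends TEAEs at the Week 100 visit anyway.

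**Step 2. Where does an event after Week 100 appear if the child never attends?**

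| Output | Population stated | Can the event appear? |
|---|---|---|
| Follow-up subject count | At least one follow-up visit | Outside the denominator; numerator not spelled out, but naturally outside |
| Follow-up event count | None; person-time to last contact | Yes, as worded |
| Pooled SAE and non-serious AE repeats | None | Yes |
| Listings | All AEs and SAEs | Yes |

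**Step 3. Size, on assumed counts.** Let N children continue into follow-up, *a* attenders have the event, *e* children have it and never attend, and *l* be lost with no event known. The plan gives a/(N − e − l). Counting everyone who continued gives (a + e)/N.

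| N | a | e | l | As written | All who continued |
|---|---|---|---|---|---|
| 300 | 3 | 1 | 0 | 3/299 = 1.00% | 4/300 = 1.33% |
| 300 | 3 | 3 | 0 | 3/297 = 1.01% | 6/300 = 2.00% |
| 300 | 3 | 5 | 0 | 3/295 = 1.02% | 8/300 = 2.67% |
| 300 | 0 | 1 | 0 | 0/299 = 0% | 1/300 = 0.33% |
| 240 | 3 | 3 | 0 | 3/237 = 1.27% | 6/240 = 2.50% |
| 300 | 3 | 0 | 30 | 3/270 = 1.11% | 3/300 = 1.00% |

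The last row has loss but no missed event, and there the written rule gives the higher percentage. If events in children outside the set were nevertheless counted in the numerator, the second row would become 6/297 = 2.02%, with three children above the line who are not below it.

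**Step 4. Disagreement between methods.** Take the second row with one event per affected child, one year of follow-up per attender and 84 days per early case (all assumed). Person-years are 297 + 3 × 84/365.25 = 297.69. The event rate as worded is 100 × 6/297.69 = 2.02 per 100 patient-years. With the visit condition imposed it would be 100 × 3/297 = 1.01. The rate table would show six events beside an incidence table with three subjects.

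**The case against.** The strongest reply is that the visit condition has a narrow reach. Much of it stands.

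- A reader might infer that such events vanish from every follow-up AE table. They do not. The condition sits within the subject-count method, and the event-count tables, pooled repeats and listings carry none.
- A reader might infer that any event before the first visit removes the child. It does not. A child who attends later is in the set, and the event counts because the window opens at Week 100. Only children who never attend are outside.
- A reader might infer that follow-up safety can only look better than it was. The last row of the Step 3 table shows the opposite for loss without an event.
- A reader might infer that the primary endpoint is touched. TEAE incidence uses all dosed subjects, with no visit condition.
- Follow-up itself is unsettled. Protocol 9.3.12 says that it is not part of this study, that the need for it is undecided and that further consent would be required. Protocol 13.1 promises a separate SAP for it. Routine AE collection ends at Visit 11 (Protocol 10.2.1.1), and the list of data after the last dose in Protocol 9.3.12 has no AE assessment. A first visit could be defended as a marker of actual entry.

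The last argument does not rescue the rule. The current SAP does plan follow-up AE tables, and Protocol 10.2.2 provides a route for related SAEs outside visits. Entry can be marked by continuation and consent, which a death cannot undo.

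**Conclusion.** The point holds for the follow-up subject-count tables. Their denominator is selected on later attendance. For deaths, and for serious events in children who never attend, the reported incidence is too low and does not match the event-count output. In the illustrations, three such children halve the figure (1.01% against 2.00%), and a single one with no events in attenders turns 0.33% into 0%.

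These sizes rest on assumed counts and on reading the numerator as confined to the set, which the SAP does not state. They are percentages only: SAP 6.4 plans exact confidence intervals for efficacy proportions, and SAP 6.5.1 plans none for AEs. The net direction in practice depends on how many non-attenders have a known event and how many are simply lost. This is a defect worth correcting in a secondary safety output, not a threat to the primary analysis.

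**What to change.** Replace the sentence in SAP 6.5.1 with:

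*The follow-up safety set is all subjects who continue into follow-up after the Week 100 visit (with the further consent where required) and have any contact or AE/SAE report, including a death or spontaneous report, after that visit, whether or not a follow-up visit took place.*

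Then:

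- use this population for both the subject-count and event-count follow-up tables, and state the denominator of the pooled tables;
- count the date of an AE or SAE report as a contact for person-time;
- show the number who continued into follow-up with no visit, and the number with no contact, with reasons.

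The cost is one sentence, one extra table row and a slightly larger denominator. The contact condition keeps children with no information from being counted as event-free, but it does not remove the effect of silent loss. With 3 events in attenders, 3 in children who never attend and 30 with no contact, the new set gives 6/(267 + 3) = 6/270 = 2.22%, against 3/267 = 1.12% as written and 6/300 = 2.00% over all who continued. The no-contact count lets a reader make that comparison.

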**Table 6.b Takeda Medically Significant AE List**

Term	
Acute respiratory failure/Acute respiratory distress syndrome (ARDS)	Hepatic necrosis
Torsade de pointes/Ventricular fibrillation/Ventricular tachycardia	Acute liver failure
Malignant hypertension	Anaphylactic shock
Convulsive seizure	Acute renal failure
Agranulocytosis	Pulmonary hypertension
Aplastic anaemia	Pulmonary fibrosis
Toxic epidermal necrolysis/Stevens-Johnson syndrome	Confirmed or suspected endotoxin shock
	Confirmed or suspected transmission of infection agent by a medicinal product
	Neuroleptic malignant syndrome/malignant hyperthermia
	Spontaneous abortion/stillbirth and fetal death

A PTE is defined as any untoward medical experience which occurs in a subject who has signed an informed consent to participate in the study but prior to the administration of any study medication; it does not necessarily have to have a causal relationship with study medication or study procedures.

If a subject is noted to have ALT or AST elevated  $>3 \times \text{ULN}$  on 2 consecutive occasions, the abnormality should be recorded as an AE, if a subject is noted to have ALT or AST  $>3 \times \text{ULN}$  and total bilirubin  $>2 \times \text{ULN}$  for which an alternative etiology has not been identified, the event should be recorded as an SAE. In addition, an abnormal Liver Function Tests (LFT) Increases eCRF must be completed.

For each study period AEs will be analyzed using the subject count method and the event count method, as described above. In each AE summary table, AEs will be presented at the MedDRA PT and SOC level. In these tables SOC levels will be listed alphabetically and under each SOC the PTs will be listed in order of decreasing frequency. Below is a list of different AE classifications to be analyzed; additional classifications may be identified later. Where appropriate, similar analyses will be produced for clinical events (i.e. those events reported during the follow up period).

- all TEAEs
- SAEs

- Repeat this analysis using all AE results for both the treatment phase and follow up phase pooled together.
  - Non serious AEs only at the PT level, overall and only those AEs meeting a minimum rate (eg. 5%)
    - Repeat this analysis using all AE results for both the treatment phase and follow up phase pooled together.
  - drug-related TEAEs
  - relationship of TEAEs to study drug (related vs. not-related)
  - severity of TEAEs (Mild, Moderate, Severe)
  - polycystic ovarian syndrome in female subjects

Data listings will be provided for all AEs including PTE, TEAEs, AEs leading to study drug discontinuation, and SAEs.

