## 6. STATISTICAL ANALYSIS

### 6.1. General Statistical Considerations

Statistical analysis will be performed using SAS® software (SAS Institute, Inc., Cary, North Carolina) Version 9.2, or later.

Unless otherwise specified, all data summaries will be performed for the following groups: Males, Females, and All Subjects. Also, where applicable, separate tables will be provided for the Treatment period (upto including Week 100 visit) and the Follow-up period. Continuous variables will be summarized including the number, the mean, the standard deviation, median, minimum and maximum. Categorical variables will be summarized including the number and percentage of subjects.

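### SAP 6.5.1 plans adverse event rates over follow-up time to last contact, although adverse events are not systematically collected after Visit 11

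*SAP*

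**What the plan says.** **Rates.** SAP 6.5.1 describes two methods: a subject count with a percentage, and an event count with a rate per 100 patient-years. It then says: "For each study period AEs will be analyzed using the subject count method and the event count method, as described above". Person-time is defined by period. For treatment: "Patient years (no. of days/365.25) for the treatment period will be determined from Day 1 to date of the Week 100 visit". For follow-up, it runs "from date of the Week 100 visit to date of last contact". The follow-up subject set is also defined: "For the follow-up period the safety set will be all subjects with at least 1 follow-up visit after the Week 100 visit". Under the SAE item, and again under the non-serious AE item, the list of analyses adds: "Repeat this analysis using all AE results for both the treatment phase and follow up phase pooled together". No pooled person-time is given.

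**AE collection after Week 100.**
- Protocol 10.2.1.1: routine collection stops at Visit 11.
- Protocol 10.2.2: after that, an SAE goes to the sponsor only if it is spontaneously reported to the investigator and considered related to study participation.
- Protocol 9.3.12, subjects still on treatment: AE assessment is listed, but recorded only where routine practice collects it.
- Protocol 9.3.12, after the last dose: the annual list has no AE item.
- SAP 3: at the annual visits "the following data will be collected if it is reported in the patients medical record: Tanner staging evaluation, height and weight measurement", then menstrual history and pelvic ultrasonography. Again there is no AE item.
- Appendix A footnote (c), in both documents: neither the on-treatment list nor the post-last-dose list names AEs.
- Appendix A schedule, in both documents: the AE assessment row is marked in the follow-up column.

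**The concern.** A rate per 100 patient-years is meaningful only if events are looked for throughout the time in its denominator. Here the denominator runs to last contact, while the documents leave event collection over that time selective or unspecified. Missed events lower the numerator and leave the denominator intact, so the rate comes out too low.

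Safety is the primary objective, and the SAP's follow-up and pooled tables would be read as long-term safety evidence. A low figure could mean missed events or a genuinely lower event rate, and the table could not show which. Subject counts that include follow-up are under-ascertained for the same reason.

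**Working it through.** The plan states no AE rate, follow-up length or capture share, so there is no figure of its own to reproduce. What follows is an illustration under stated assumptions.

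**Inputs from the documents.** N = 300 (SAP 4). Week 100 is Day 700 (SAP 6.2.3, Table 6.a). Patient-years are days/365.25 (SAP 6.5.1).

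**Assumed.** All 300 subjects reach Day 700. Mean follow-up is 1 to 4 years for all 300, so F = 300 to 1200 patient-years. The share of follow-up events captured is c. The true follow-up rate is r times the treatment-period rate. Pooled person-time is the sum of the two periods.

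**Step 1, treatment person-time.** T = 300 × 700 / 365.25 = 574.9 patient-years.

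**Step 2, stand-alone follow-up rate.** Reported/true = c, whatever F and r are. It is 0.50 at 50% capture and 0.80 at 80%.

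**Step 3, pooled rate.** Reported/true = (T + c·r·F) / (T + r·F).

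| r | c | F = 300 | F = 1200 |
|---|---|---|---|
| 1 | 0.5 | 724.9/874.9 = 0.83 | 1174.9/1774.9 = 0.66 |
| 1 | 0.8 | 814.9/874.9 = 0.93 | 1534.9/1774.9 = 0.86 |
| 0.5 | 0.5 | 649.9/724.9 = 0.90 | 874.9/1174.9 = 0.74 |
| 0.5 | 0.8 | 694.9/724.9 = 0.96 | 1054.9/1174.9 = 0.90 |

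At c = 1 every ratio is 1. Treatment events, which are routinely collected, dilute the shortfall, so the pooled rate is less affected than the stand-alone follow-up rate.

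**Step 4, missed events against a lower true rate.** Relative to the treatment-period rate, the reported pooled rate is (T + c·r·F) / (T + F), which depends only on the product c·r. Half capture of an equal rate (c = 0.5, r = 1) and full capture of a halved rate (c = 1, r = 0.5) both give 0.83 at F = 300 and 0.66 at F = 1200.

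**Step 5, how far the direction depends on the denominator.** Take F = 600 (2 years) and r = 1.
- Pooled events over treatment time only, c = 0.5: (574.9 + 300)/574.9 = 1.52 of true, an overstatement.
- Summed time with 15% of treatment time lost (assumed) but its events kept, c = 0.9: (574.9 + 540)/(0.85 × 574.9 + 600) = 1.02 of true.

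The understatement of the pooled rate therefore holds for summed, complete person-time. The follow-up rate needs no such condition, because the SAP writes its person-time rule out.

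**The case against.** **The pooled tables do have a default subject denominator.** A reader might infer that none exists. SAP 6.5 says safety data use the safety analysis set, which SAP 5 defines as all enrolled subjects with at least one dose. The separate follow-up set is an exception for follow-up tables. This stands: only the pooled person-time is open.

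**A pooled rate is not written.** The two methods are prescribed by study period, and pooled data are not a study period. The example 5% cut-off for non-serious AEs is a percentage and fits the subject count. This stands, so the statement about the pooled rate is conditional. A reader might also infer that any pooled rate must be too low; step 5 shows that this depends on the denominator.

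**Follow-up may never happen.** Protocol 9.3.12 says it is outside this study, not yet decided, and would need fresh consent. Protocol 13.1 promises a separate SAP. This stands as a condition. But Protocol 13.2 and SAP 6.7 say the study continues into follow-up, and this SAP itself specifies the follow-up and pooled analyses.

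**The collection passages can partly coexist.** An end to routine collection is compatible with later recording of what practice yields, and the lists without AEs are mainly clinical measurements. That softens the conflict but confirms that capture is not systematic.

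**Separation by period is already planned.** SAP 6.1 states: "Also, where applicable, separate tables will be provided for the Treatment period (upto including Week 100 visit) and the Follow-up period". SAP 6.5.1 classes later AEs as clinical events and lists all AEs. This stands.

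**Further readings that the documents do not support.** One is that the primary result is compromised: TEAE incidence and the treatment-period tables do not use follow-up events or time. Another is that terms would vanish under the 5% cut-off: the cut-off is only an example, and the SAP asks for an overall table too. A third is that early leavers in general have no end date for treatment person-time: Table 6.a and Appendix A label Visit 11 as the Final Safety or Early Termination Visit, so essentially only subjects with no Visit 11 are left undefined.

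**Conclusion.** The concern holds in a limited form. If follow-up takes place, the SAP's follow-up rate counts person-time over which AEs are not systematically collected, and it understates the true rate whenever events are missed. A pooled rate shares the defect, diluted, if it is produced with the two periods' patient-years summed.

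The size cannot be fixed from the documents. At 50% capture and equal true rates, the illustration gives 0.50 of true for follow-up and 0.83 to 0.66 pooled. At 80% capture it gives 0.80, and 0.93 to 0.86. A lower true follow-up rate, or fewer subjects in follow-up, would shrink the pooled error; less treatment time would enlarge it. Complete capture would remove it.

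The study is descriptive and its primary endpoint is untouched. The SAP should still be changed, because the correction is cheap and the uncorrected rate could be read as reassuring.

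**What to change.** In SAP 6.5.1:

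1. Give no rate per 100 patient-years for follow-up clinical events or in the pooled tables, unless person-time is limited to time under active AE collection.
2. In the pooled SAE and non-serious AE tables, show event counts and subject counts over the safety analysis set, labelled as incompletely ascertained after Visit 11. Keep the separate period tables already planned.
3. As a minor clarification, end treatment-period patient-years at the Visit 11 date, whether Week 100 or Early Termination. With no Visit 11, end them at the earlier of last contact and last dose + 29 days, the limit of the TEAE window (onset − last dose + 1 ≤ 30).

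Across the documents, reconcile Protocol 9.3.12, 10.2.1.1 and 10.2.2, the Appendix A schedule and footnote (c) in both documents, and SAP 3 on whether and how AEs are collected in follow-up.

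The cost is SAP wording, some programming and a short protocol clarification. No new data are needed. The downside is the loss of a rate display for follow-up and pooled data, unless time under active collection can be identified.
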